- 3. Addition of Heparinase to *INTEM* assay, can help to discriminate heparin activity from an enzymatic factor deficiency: **HEPTEM test.**

Some other parameters can also be assessed by ROTEM. These include: clotting time, clot formation time, clot firmness, clot lysis, and A10 (which measures the amplitude at 10 minutes after the end of clotting time).

Several studies in trauma, cardiac surgery, postpartum hemorrhage, and scoliosis surgery have shown that maximum clot firmness (MCF) and fibrinogen levels are excellent predictors of perioperative bleeding complications and massive transfusion.[12] FIBTEM-A10 (Clot amplitude at 10 minutes after the end of clotting time) and FIBTEM MCF (maximum clot firmness) predict massive transfusion similarly to standard coagulation tests [13].

In cardiac surgeries, POC testing showed a lower cumulative dosage of packed erythrocytes, lower rate and smaller dose of fresh frozen plasma (FFP) and platelets concentrate (PC) transfusion. As well as reduced postoperative mechanical ventilation time, length of intensive care unit stay, composite adverse events rate, cost of hemostatic therapy, and 6-month mortality [3].

ROTEM standardized massive transfusion protocols have been used to successfully choose the optimal allogeneic blood product or coagulation factor concentrate, reduce transfusion requirements and reduce blood loss in cardiac surgery, transplant surgery, and massive trauma. The rapid ROTEM turnover has shown to impact a timely targeted hemostatic therapy and coagulopathy prevention [11, 14, 15].

Protocol #:2014H0447

Version: 1.0

The choice and amount of haemostatic therapy is not only highly relevant for patient outcomes but it is also highly relevant economically. Transfusion cost-benefit analysis has shown that the average cost of allogeneic blood replacement is \$250 per unit transfused, auto transfusion is \$270 per individual, and cell saver is \$512 per patient [11]. Recently, the analysis of the cumulative cost of hemostatic therapy comparing POC-guided therapy with conventional coagulation test guided therapy found that the mean cost of therapy is $1,528 \in (\$1,924)$ and $3,109 \in (\$3,914.76)$ per patient respectively [3].

II. OBJECTIVES

1. Primary objective

Compare the overall amount of intra-operative Red Blood Cells and Fresh Frozen Plasma guided with ROTEM versus laboratory coagulation tests in patients undergoing major spinal surgeries.

2. Secondary objectives

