The power analysis has been calculated based on a mean estimated RBC transfusion of 8 units with a conservatively estimated standard deviation of 5. We expect that ROTEM will decrease the RBC transfusion by 3 units. We make the same assumptions for FFP. We will test each main outcome between the ROTEM and control groups at an alpha of 0.025 (adjusted for 2 main outcomes). We need 110 patients; 55 patients in each group to achieve 80% power to detect a difference of 3 units assuming a standard deviation of 5 at an alpha of 0.025.[3,13]

4. Randomization and study procedures:

Patients will be randomized in a 1:1 ratio to either laboratory coagulation tests or ROTEM. No changes in surgery or anesthesia technique will be made for study's purposes.

a. Laboratory Coagulation Tests

If the patient is randomized to laboratory coagulation tests, anesthesia care providers will assess the hemostatic status according to OSUWMC standard practices and their own clinical criteria.

Laboratory coagulation tests include but are not limited to the following: hemoglobin, platelet count, fibrinogen concentration, INR, aPTT, and PT. These assessments will be performed at fixed perioperative time points (preoperatively, every 2 hours intraoperatively, end of surgery (EOS), and 24 hours after EOS). Intraoperative arterial blood gases will be performed repetitively

Protocol #:2014H0447 Version: 1.0 at a fixed range (every hour) based on anesthesia care provider's decision, along with any other common laboratory tests.

b. ROTEM

If the patient is randomized to ROTEM, the anesthesia care provider will be blinded to any conventional intraoperative coagulation test that might be performed during surgery.

ROTEM will be used according to the manufacturer's instructions using equipment and test reagents provided by Tem International GmbH. All tests will be performed at the bedside by a healthcare provider trained to perform ROTEM. A specific algorithm has been created by [name] (Clinical Director at Tem International GmbH-ROTEM) and should be followed according to measurements obtained during surgery (Figure 1).

ROTEM monitoring will be performed in patients with signs of clinically relevant diffuse bleeding and in whom blood transfusion is considered (Temp >35°C; pH <7.2; Cai >4.6 mg/dL; Hb \ge 9g/dL, or >10g/dL with anticipated greater blood loss) or at a fixed range every 2 hours or at Anesthesiologist criteria based on patient's clinical situation.

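### RBC and FFP are each held to a fixed 0.025; Holm's procedure would add power at the same 110 patients and the same 5% family-wise limit

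*Combined protocol and SAP*

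**What the plan says.** Section II.1 (Primary objective) names two products together: "Compare the overall amount of intra-operative Red Blood Cells and Fresh Frozen Plasma guided with ROTEM versus laboratory coagulation tests".

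Section III.3 (Study population and sample size) plans on a "mean estimated RBC transfusion of 8 units with a conservatively estimated standard deviation of 5" and adds: "We expect that ROTEM will decrease the RBC transfusion by 3 units". For the second product it says only: "We make the same assumptions for FFP". The size follows: "We need 110 patients; 55 patients in each group to achieve 80% power to detect a difference of 3 units". The multiplicity rule is: "We will test each main outcome between the ROTEM and control groups at an alpha of 0.025 (adjusted for 2 main outcomes".

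The documents give no step-down, gatekeeping or alpha-recycling rule. They do not name the test or say whether it is one- or two-sided. They write only the per-outcome 0.025; the 5% total is implied by 2 × 0.025. No power target is set for showing an effect on both products.

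**The concern.** A fixed split holds the second product to 0.025 even after the first has succeeded. At that point the unused part of the 5% can be passed on without exceeding the family-wise limit, and the plan does not do so.

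This matters because the objective names both products. Under the plan's own assumptions, the fixed split has a 24 to 35% chance of missing at least one of them (100 − 75.8 and 100 − 65.2). With Holm that falls to 18 to 24% (100 − 82.3 and 100 − 76.4). FFP may be the more exposed of the two, since its planning figures are carried over from RBC. What is at stake is efficiency, not validity.

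**Working it through.** **Inputs.** From Section III.3: difference 3 units, SD 5, alpha 0.025 per outcome, 55 per arm, and the same figures for FFP. From Section III.4: 1:1 allocation. Assumed here: two-sided t-tests, approximately normal data, and an RBC–FFP correlation between 0 and 0.9.

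**Step 1: the plan's own figure.** The standardised difference is 3/5 = 0.6. The normal approximation is n = 2(z₀.₉₈₇₅ + z₀.₈₀)²/0.6² = 2(2.241 + 0.842)²/0.36 ≈ 52.8, so 53 per arm. The t-test (noncentral t) needs 54.08, so 55 per arm. Power is 79.9% at 54 and 80.7% at 55. A one-sided test at 0.025 would need only 45 per arm (80.4%), so the stated size implies two-sided testing. The plan's 110 reproduces.

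**Step 2: the fixed split is valid.** The bound is 2 × 0.025 = 0.05. With independent outcomes the family-wise error is 1 − 0.975² = 0.0494.

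**Step 3: Holm at correlation 0, by formula.** Holm tests the smaller p-value at 0.025 and, if that is significant, the other at 0.05. Let P₁ = 0.8074 (power at 0.025) and P₂ = 0.8766 (power at 0.05), both at 55 per arm.

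- Per outcome: P₁ + (P₂ − P₁)P₁ = 0.8074 + 0.0692 × 0.8074 = 0.863, against 0.807.
- Both: P₁² + 2P₁(P₂ − P₁) = 0.652 + 0.112 = 0.764, against 0.652.

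**Step 4: other correlations, by simulation** (bivariate normal data, t-tests, 55 per arm, difference 3 and SD 5 on both). Power per outcome under the fixed split is 80.7% throughout.

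| Correlation | Per outcome, Holm | Both, fixed | Both, Holm | At least one, either method |
|---|---|---|---|---|
| 0 | 86.3% | 65.2% | 76.4% | 96.3% |
| 0.3 | 85.7% | 67.6% | 77.7% | 93.8% |
| 0.5 | 85.3% | 69.7% | 78.9% | 91.8% |
| 0.8 | 84.5% | 73.7% | 81.3% | 87.8% |
| 0.9 | 84.0% | 75.8% | 82.3% | 85.7% |

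The gain is 3.3 to 5.6 points per outcome and 6.5 to 11.2 points for both. When neither product differs, family-wise error is the same under both methods: 4.9% at correlation 0, falling to 3.6% at 0.9.

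**Step 5: what the gain is worth in patients.** For the same per-outcome power the fixed split needs about 60 per arm (84.4%) to 64 per arm (86.8%). That is 2 × 5 = 10 to 2 × 9 = 18 more patients.

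**Step 6: a smaller FFP effect, with RBC still at 3 units.**

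| True FFP difference | Gain for RBC | FFP rejected, fixed | FFP rejected, Holm |
|---|---|---|---|
| 2 | 0 to 3 points | 43% | 53–54% |
| 1.5 | 0 to 2 points | 25% | 33–34% |
| 0 | at most 0.2 points | 2.5% (false positive) | 3.8–4.5% (false positive) |

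**Step 7: skewed whole-unit data.** With gamma-distributed counts rounded to whole units (means 8 and 5, SD 5), per-outcome power rises from about 80% to 84–86%, and power for both from 64–75% to 75–81%. The gain does not depend on normality.

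**The case against.** The strongest reply is that nothing is broken. The adjustment is stated, the size reproduces, the 80% target per outcome is met, no target for both is set, and the chance of at least one positive result is unchanged. All of that stands, and it is why this is an optional improvement.

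Two costs also stand.

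- **Intervals.** Every extra rejection under Holm has a p-value between 0.025 and 0.05, so its 97.5% interval includes zero. The gain for both (6.5 to 11.2 points) and the rate of such conflicts are therefore the same trials. If the FFP difference is 2, the conflict rate is the sum of the two per-outcome gains: 3.0 + 9.2 = 12.2% at correlation 0 and 0.1 + 11.1 = 11.2% at 0.9. Under the fixed split, test and interval always agree.
- **Error on a null product.** If RBC differs and FFP does not, the false-positive rate on FFP is the family-wise error. It rises from 2.5% to as much as 4.5% (4.5/2.5 = 1.8 times), while RBC gains almost nothing. The 5% ceiling holds, but the actual error is higher.

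It is also true that the size of the gain rests on a correlation the plan does not give and on both effects being as large as planned, and that the plan names no test to produce the p-values. These points limit the size of the benefit. They do not alter the fact that Holm never rejects less than the fixed split and stays within 5% at any correlation.

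**Conclusion.** The point holds as a cheap improvement, not as an error. The fixed 0.025 per outcome is valid and delivers the 80% the plan states. At the same 110 patients and the same 5% family-wise limit, Holm adds about 3 to 6 points of power per outcome and about 6 to 11 points for showing both.

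That size assumes a true difference of 3 units and SD 5 on both products, two-sided t-tests and a correlation of 0 to 0.9. With a smaller FFP effect the benefit goes mainly to FFP; with none, it nearly disappears. That Holm rejects at least as often, and that it controls the error at 5%, needs none of these assumptions.

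**What to change.** In Section III.3, replace the sentence on alpha with:

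> RBC and FFP are tested by the Holm procedure at a two-sided family-wise error of 5%: the smaller p-value is tested at 0.025 and, if significant, the other at 0.05.

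Also name the test that produces the p-values. Report 97.5% confidence intervals for both differences. State in advance that the second interval may include zero although Holm rejects, and that the Holm result then decides significance.

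Make the change before anyone sees outcome data by arm. The documents do not show whether recruitment has begun, and the treating anesthesia staff know the arm, so the date of the change should be recorded.

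The size stays at 110, and 80% per outcome remains as a minimum. The cost is one sentence plus the possible conflict between test and interval. If the sponsor values intervals that always match the tests, the fixed split can be kept with that reason written down.

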Patient's clinical situation should be consider as the most important component on the transfusion decision-making process. Packed erythrocytes will be transfused to maintain hemoglobin concentrations >9g/dl or >10g/dl in individuals with underlying cardiovascular disease or anticipated greater blood loss. Individual based dynamics (tachycardia, hypotension, sings of ischemia on electrocardiogram, and lactic acidosis) strongly indicating the need for erythrocyte transfusion will be also part of the decision-making transfusion process by the anesthesia care provider.

5. Data collection

The following data points will be recorded in the interventional and control group patients:

- Demographic information (age, sex, height, weight, BMI, race)
- Medical History (including past and current diagnosis, use of chemotherapy or radiation, type of cancer, medications, surgical history)
- Surgical Information (Procedure type/reason for surgery, length of surgery, perioperative medications, ASA physical classification, type of anesthesia)
- Anesthesia record information
- Baseline (pre-operative) and perioperative coagulation lab values (PT, PTT, INR, HTC, HTC, PLT, FIB) (followed for 24 hours postoperatively)
- Perioperative ROTEM values
- Baseline and perioperative hemodynamics (BP, HR, RR, OXYGEN SATURATION, Temperature).
- Intraoperative arterial blood gases
- Intraoperative blood loss (over time)

Protocol #:2014H0447

Version: 1.0

- Transfusion information (type of product, number of transfused units, time administered) intraoperative and 6, 12, and 24 postoperative.
- Use of other hemostatic therapy
- Use of antifibrinolytic agents
- Intraoperative fluid management (type, volume, and frequency)
- Urine output for the first 24 hours.
- Postoperative time of mechanical ventilation
- Length of ICU stay and hospital stay
- Other intraoperative and postoperative complications (including respiratory failure, overall infection rate)
- Inpatient mortality
- Postoperative Day 30 phone call follow-up to assess serious adverse events and mortality.
- Hemostatic therapy cost assessment

IV. Assessment and reporting of Adverse Events and Serious Adverse Events

The occurrence of adverse events (AE) and serious adverse events (SAE) will be recorded from the time of consent until discharge. For each AE, the relationship to the study procedures and monitoring, severity, expectedness, outcome will be determined by the PI and recorded in the study source accordingly

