- The subject requests to be discontinued from the study

- A protocol violation sufficiently serious as to require subject withdrawal

[figure not shown]
- General or specific changes in the subject's condition that render further treatment unreasonable or unsafe within the standards of clinical practice in the judgment of the Principal Investigator or treating physician.

Any subject may leave the study at any time. If a subject decides to stop participating in the study, there will be no penalty. The subject will not lose any benefits to which they are otherwise entitled. Their decision will not affect their future relationship with The Ohio State University.

Protocol #:2014H0447

Version: 1.0

VI.Figure 1. ROTEM Spine Surgery Algorithm

- ¹ Basic conditions:
 - Temp. >35°C; pH >7.2; Cai++ >4.6 mg/dL.
 - $Hb \ge 9 g/dL$.
- ² Antifibrionolytic therapy:
 - Dirkmann et al. Anesth Analg. 2014 (under review)
 - CT_{FIB} > 600 s represents a flat-line in FIBTEM
 - Chapman et al. J Trauma Acute Care Surg. 2013
- ³ Fibrinogen dose calculation:

- A10_{FIB} 9-12 mm: 50 mg/kg fibrinogen
 (2.5 mL/kg fibrinogen conc. or 5 mL/kg cryoprecipitate)
- A10_{FIB} ≤ 8 mm: 75 mg/kg fibrinogen
 (3.75 mL/kg fibrinogen conc. or 7.5 mL/kg cryoprecipitate)
- ⁴ Platelet concentrate (PC) transfusion:
 - A10_{EX} 35-44 mm: 1 pooled or apheresis PC
 - \circ A10_{EX} < 35 mm: 2 pooled or apheresis PC
 - A10_{EX} \leq 25 mm: Platelet conc. + fibrinogen
- ⁵ If Prothrombin-Complex-Concentrate (PCC) is not available:
 - o 10-15 mL/kg FFP or
 - \circ 45-90 µg/kg rFVIIa (if A10_{EX} and A10_{FIB} are ok but FFP is not effective)
- Simultaneous interventions:
 - Maximum three interventions at the same time (In first analysis and severe bleeding)
 - Maximum two interventions at the same time (In second analysis and moderate to severe bleeding)
 - Only one intervention
 (In second or later analysis and mild to moderate bleeding)

Version: 1.0

Protocol #:2014H0447

Version: 1.0

VIII. REFERENCES

- 1. Bilsky, M.H. and J.F. Fraser, *Complication avoidance in vertebral column spine tumors*. Neurosurg Clin N Am, 2006. **17**(3): p. 317-29, vii.
- 2. Elgafy, H., et al., *Blood loss in major spine surgery: are there effective measures to decrease massive hemorrhage in major spine fusion surgery?* Spine (Phila Pa 1976), 2010. **35**(9 Suppl): p. S47-56.

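### The primary comparison names no baseline covariates although relevant pre-operative values are already recorded in both arms: a modest gain in precision is missed, but the sample size is not wrong and there is no bias

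*Combined protocol and SAP*

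**What the plan says.** Section III.3 (Study population and sample size) holds the only analysis statement for the two main outcomes: "We will test each main outcome between the ROTEM and control groups at an alpha of 0.025 (adjusted for 2 main outcomes"). It names no test, model, covariate or stratification factor. The sample size rests on a "mean estimated RBC transfusion of 8 units with a conservatively estimated standard deviation of 5", with the same assumptions for FFP, and concludes that the trial needs "55 patients in each group to achieve 80% power to detect a difference of 3 units assuming a standard deviation of 5". Section III.1 describes a computer-generated 1:1 list and nothing further.

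Elsewhere the protocol links these outcomes to things known before surgery:

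- Section III.4: "Packed erythrocytes will be transfused to maintain hemoglobin concentrations >9g/dl", with a higher level for some patients and with clinical judgement alongside.
- Background: clot firmness and fibrinogen levels are described as very good predictors of bleeding complications and massive transfusion, with scoliosis surgery among the settings named.
- Figure 1, note 5: a per-kilogram plasma line, "10-15 mL/kg FFP or" an alternative product, for use when PCC is not available.

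Section III.5 (Data collection) lists, for both arms, "Baseline (pre-operative) and perioperative coagulation lab values (PT, PTT, INR, HTC, HTC, PLT, FIB") and "Demographic information (age, sex, height, weight, BMI, race"). HTC is read here as haematocrit. No analysis is said to use any of these values.

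**The concern.** If starting haematocrit, body size or fibrinogen predicts how many units a patient receives, an analysis that ignores them leaves that predictable variation in the error term. The standard error is then larger than it need be. A chance imbalance between arms in starting haematocrit, for example, also feeds into the estimated difference in units, and a plain comparison has no way to remove it.

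The trial was sized to just reach its target, so a modest gain in precision would be useful, and the data for it are already being collected. Silence on adjustment has a second cost: it leaves the choice of covariates open until results are known.

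**Working it through.** **Inputs from section III.3.** Difference 3 units; SD 5; alpha 0.025 per outcome; 55 per arm (N = 110). Sidedness is not stated. Two-sided is assumed, because one-sided 0.025 would need only about 45 per arm by t-test.

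**Step 1: reproduce the plan's figure.** Standardised difference = 3/5 = 0.6. A two-sample t-test at two-sided 0.025 and 80% power needs 54.08, so 55 per arm and 110 in total. Power at 55 per arm is 80.7%. The standard error of the difference is 5 × √(2/55) = 0.953 units. The stated 110 is therefore exactly what an unadjusted comparison on the raw SD requires.

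**Step 2: the gain from covariates.** If baseline covariates explain a share R² of the outcome variance, the residual SD is 5 × √(1 − R²). The documents give no R², so a range is assumed. Ignoring any cost of adjustment, power at 55 per arm would be 82.9%, 85.0% and 89.2% for R² of 0.05, 0.10 and 0.20.

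**Step 3: the cost of covariates.** Each of k covariates uses a degree of freedom and, more importantly, is correlated with arm by chance in any one randomisation. On average the variance is multiplied by (N − 3)/(N − k − 3):

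- k = 2: 107/105, so the SE rises by a factor of √1.0190 = 1.009.
- k = 3: 107/104, so the SE rises by a factor of √1.0288 = 1.014.

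Counting only the lost degrees of freedom would miss nearly all of this cost.

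**Step 4: net power.** This uses the noncentral t with N − 2 − k degrees of freedom, averaged over the chance imbalance. The share of arm variance explained by k unrelated covariates is taken as Beta(k/2, (N − 1 − k)/2).

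| Assumed R² | Unadjusted | 2 covariates | 3 covariates |
|---|---|---|---|
| 0 | 80.7% | 79.9% | 79.5% |
| 0.05 | 80.7% | 82.1% | 81.7% |
| 0.10 | 80.7% | 84.2% | 83.9% |
| 0.20 | 80.7% | 88.5% | 88.2% |

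Adjustment breaks even with the unadjusted 80.7% at an R² of about 0.02 with two covariates and 0.03 with three.

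**Step 5: the same result in patients.** The 110 patients would be worth 110/(1 − R²) × (107 − k)/107 in an unadjusted analysis, where 107 − k is 105 or 104:

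- R² = 0.05: 113-114 patients
- R² = 0.10: 119-120 patients
- R² = 0.20: 134-135 patients

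**The case against.** The case against has real substance.

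- **Nothing is invalid as it stands.** A reader might infer that the trial is underpowered, or that its result would be biased without adjustment. The documents support neither. The stated 110 reproduces, its 80% power holds under the plan's assumptions, and an unadjusted comparison of randomised arms is unbiased with a standard error that already allows for chance imbalance.
- **The gain may be small.** The background quotes blood losses from 650 to 2839 mL in spinal fusion and from 1100 to 6039 mL in metastatic disease, and the inclusion criteria admit spinal, orthopedic and combined procedures. If blood loss dominates, pre-operative values may explain only a few per cent of the variance, which is close to break-even.
- **Weight does not drive FFP across the trial.** The per-kilogram line in Figure 1 might be read as making plasma units proportional to weight. It belongs to the ROTEM algorithm alone, applies only when PCC is unavailable, and has an alternative beside it. Control-arm care follows institutional practice and the provider's own criteria.
- **The haemoglobin rule is soft.** Section III.4 gives the clinical situation first place and adds haemodynamic and ischaemic signs. The rule also appears under the ROTEM heading, and its use in controls is not spelled out.
- **The plan is silent; it does not refuse adjustment.** That the test is unadjusted is an inference from the wording and from Step 1. Section numbering in the text available runs from VI to VIII, so a further section cannot be excluded.

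These points limit the size of the gain and weaken the argument for weight in the FFP model. They do not remove the case for using haematocrit and fibrinogen, which the plan records and links to bleeding or transfusion.

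**Conclusion.** The point holds as a missed gain in precision. The plan specifies a between-arm test sized on the raw SD and gives no analytic role to pre-operative predictors that it collects in both arms. With two to three covariates, power at 55 per arm moves from 80.7% to about 82%, 84% or 88% at an R² of 0.05, 0.10 or 0.20. If the covariates are useless it falls by about 1 point, to 79.5-79.9%.

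These figures assume a two-sided test, the plan's difference and SD, and an R² that cannot be taken from the documents. It would be going too far to call the precision free: there is a small cost, and adjustment pays only above an R² of roughly 2-3%. The change is worth making, mainly because the possible gain exceeds the possible loss and because fixing the covariates in advance closes an open choice. The trial's validity does not depend on it.

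**What to change.** In section III.3, name the primary analysis of each main outcome as a linear regression with robust standard errors, with these terms:

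- **RBC units:** arm, pre-operative haematocrit, and weight (or blood volume estimated from sex, height and weight).
- **FFP units:** arm and pre-operative fibrinogen. Weight is optional, given the limited reach of the per-kilogram line.

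Report the adjusted mean difference in units with a 97.5% confidence interval for each outcome, and give the unadjusted difference as a sensitivity analysis. Keep 110 patients and 0.025 per outcome, and state that the test is two-sided if that is intended. Allow only pre-operative covariate values. Intra-operative measurements such as blood loss can be affected by the allocated strategy and must not be adjusted for. State when the baseline sample is taken relative to randomisation, which the protocol does not say, and give a simple rule for a missing baseline value.

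The cost is a short protocol amendment: no new data, visits or patients, one to three degrees of freedom per model, and the roughly 1-point loss of power in the worst case.

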- Compare the amount of Cryoprecipitate and Platelets transfused intraoperative between both groups.
- Compare the amount of all blood products transfused at 6, 12, and 24 hours postoperative.
- Compare the incidence and requirements of fibrinogen concentrate, PCC, antithrombin concentrate, factor XIII concentrate, and activated recombinant factor VII, or any other hemostatic therapy. Compare variables that affect coagulopathy such as acidosis and hypothermia.
- Compare hemodynamic variables (BP, HR, O2, Temperature, Arterial blood gases) during surgery.
- Compare postoperative time of mechanical ventilation
- Compare length of ICU stay and overall hospital stay
- Compare total in hospital need for transfusion
- Compare postoperative coagulation status on days 1 and 3 if available
- Compare overall infection rate
- Compare 30 days mortality

3. Exploratory objectives

Compare the total costs of intra-operative blood transfusion guided with ROTEM versus laboratory coagulation tests in patients undergoing major spinal surgeries.

III. Material and methods

1. Study design:

This is a prospective, randomized parallel-group, single center study in patients undergoing elective major spine surgery. Patients will be randomized to guide blood transfusion administration with ROTEM or laboratory coagulation tests (ABG, PT, PTT, aPTT, Hb, platelets,

Version: 1.0

and fibrinogen). Randomization list will be computer-generated using a balanced allocation ratio 1:1.

- 2. Inclusion and exclusion criteria:
- Inclusion criteria
- 1. Male or female age 18 years or older.
- 2. Able to provide inform consent.
- 3. Patients schedule to undergo elective major spinal, orthopedic, or combined procedures under general anesthesia that are expected to receive intraoperative blood products and last greater than 2 hours.
- Exclusion criteria
 - 1. Subjects younger than 18 years old.
 - 2. Subjects who are prisoners.
 - 3. Subjects who refuse transfusion of blood products.
 - 4. Subjects unable to participate in the study for any reason in the opinion of the Principal Investigator.
 - 5. Subject with past medical history of uncontrolled coagulopathies.

3. Study population and sample size:

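### Conventional laboratory and blood-gas sampling is scheduled for the laboratory arm only, so the secondary acidosis, blood-gas and day 1 coagulation comparisons may be ascertained differently by arm

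*Combined protocol and SAP*

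**What the plan says.** Section III.4.a, for patients randomized to laboratory tests, lists hemoglobin, platelets, fibrinogen, INR, aPTT and PT and then states: "These assessments will be performed at fixed perioperative time points (preoperatively, every 2 hours intraoperatively, end of surgery (EOS), and 24 hours after EOS". On blood gases it says "Intraoperative arterial blood gases will be performed repetitively", and continues after a page break: "at a fixed range (every hour) based on anesthesia care provider's decision, along with any other common laboratory tests".

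Section III.4.b, for the ROTEM arm, schedules ROTEM itself: on clinically relevant bleeding, every 2 hours, or at the anesthesiologist's judgement. Conventional tests appear only in the statement that "the anesthesia care provider will be blinded to any conventional intraoperative coagulation test that might be performed during surgery". No interval is given for conventional tests or blood gases in this arm.

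Section II.2 plans between-arm comparisons that rest on these measurements: "Compare variables that affect coagulopathy such as acidosis and hypothermia" and "Compare hemodynamic variables (BP, HR, O2, Temperature, Arterial blood gases) during surgery". It also compares postoperative coagulation status on days 1 and 3, where available.

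Section III.5 lists coagulation laboratory values (baseline, perioperative and to 24 hours after surgery) and intraoperative blood gases as data to be recorded in both arms. It sets no interval.

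**The concern.** A comparison of measured values between arms is interpretable when the values are obtained on the same plan in both. If one arm is sampled by the clock and the other when a clinician sees a reason, two distortions are possible, and they need not point the same way. More draws give more chances to find an abnormal value. Draws taken on suspicion tend to catch patients when they are worse, which shifts means and extremes. Either could produce an apparent difference in acidosis or blood gases with no difference in physiology, or could hide a real one.

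The text gives no summary measure for these comparisons and no rule for unequal numbers of values per patient, so the analysis as written offers no protection. At stake is the reading of several named secondary comparisons.

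**Working it through.** **Sampling plan by arm**

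| Item | Laboratory arm (III.4.a) | ROTEM arm (III.4.b) | Both-arm list (III.5) |
|---|---|---|---|
| Conventional laboratory tests | Preoperative, 2-hourly, end of surgery, 24 hours later | Possible; no interval | Baseline, perioperative, to 24 hours; no interval |
| Blood gases | Hourly, but at the provider's decision | No interval | Listed; no interval |
| ROTEM | None stated | Bleeding, 2-hourly, or clinician's judgement | Perioperative values listed |

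Section III.1 supports reading the III.4.a times as specific to that arm, because it names blood gases, hemoglobin, platelets and fibrinogen among the tests that make up the laboratory-guided strategy.

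**Which outcomes depend on it**
- Acidosis and intraoperative blood gases (II.2): yes.
- Coagulation status on day 1: yes, because the draw 24 hours after surgery has a stated time only in III.4.a.
- Coagulation status on day 3: no difference between arms, because neither has a day 3 draw scheduled.
- The 2-hourly intraoperative coagulation tests: no listed coagulation-status outcome uses them.
- RBC and FFP units: not measured by these tests. The plan's one computed figure, 55 per group, reproduces and is unaffected. A two-sample t-test with two-sided alpha 0.025, 80% power and effect size 3/5 = 0.6 needs 54.08, rounded up to 55.

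**Can the size be computed?** No. The documents give no blood-gas count for the ROTEM arm, no acidosis rate and no within-patient correlation. What follows is illustration only, with the same true risk in both arms. It uses an at-least-one-abnormal-value measure, which the plan does not specify. Let *p* be the chance that one draw is abnormal and *k* the number of draws.

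Independent draws, P = 1 − (1 − p)^k:
- p = 0.10, 5 v 2 draws: 1 − 0.9^5 = 41.0%; 1 − 0.9^2 = 19.0%; gap 22.0 points.
- p = 0.05, 5 v 2 draws: 22.6% v 9.8%; gap 12.9 points before rounding.
- p = 0.20, 5 v 2 draws: 67.2% v 36.0%; gap 31.2 points.
- p = 0.10, 5 v 4 draws: 41.0% v 34.4%; gap about 6.6 points.
- Equal counts: gap 0.

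Correlated draws: a beta-binomial with within-patient correlation 0.5 and p = 0.10 has parameters a = 0.1 and b = 0.9, because a + b = 1/0.5 − 1 = 1. The chance of no abnormal value is the product of (b + i)/(a + b + i) for i from 0 to k − 1:
- k = 2: 0.9 × 0.95 = 0.855, so 14.5% have at least one.
- k = 5: 0.855 × (2.9/3) × (3.9/4) × (4.9/5) = 0.790, so 21.0% have at least one.
- Gap 6.5 points.

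Serial pH values in one patient during one operation are unlikely to be independent. The answer depends heavily on the draw counts and the correlation, and the documents give neither.

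**The case against.** The strongest reply is that unequal sampling is inferred from silence. III.5 requires these values to be recorded in both arms. The ROTEM algorithm's basic conditions include pH, ionized calcium and hemoglobin, so blood gases will probably be drawn in that arm too. The hourly interval in III.4.a is itself subject to the provider's decision, so blood gases may be discretionary in both arms.

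Much of this stands. A reader might infer that controls will be sampled more often. The documents do not say so, and the blood-gas wording does not establish it. What the reply does not supply is a time plan for the ROTEM arm. Recording whatever was drawn does not equalise when it was drawn, and measurements taken alongside bleeding-triggered ROTEM may be prompted by the patient's state.

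A reader might also infer that the RBC co-primary is biased, because hemoglobin and lactic acidosis inform the transfusion decision. The documents do not support that. Units are recorded as transfusion data in both arms, and nothing shows that hemoglobin or lactate is less available in one of them. Any difference in the information guiding transfusion is arguably part of the strategies under comparison.

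Finally, the plan nowhere defines acidosis as at least one episode. The illustrations therefore do not carry over directly to a comparison of means or of values at set times.

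**Conclusion.** The point holds in a limited form. An interval for conventional tests and blood gases is stated for one arm only, the blood-gas sentence is both fixed and discretionary, and nothing in the analysis handles unequal sampling. The secondary comparisons of acidosis, intraoperative blood gases and day 1 coagulation status may therefore be ascertained differently by arm.

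The direction is unknown and the size cannot be derived from the documents. Gaps of 0, about 6.5 or about 22 points all follow from plausible-looking assumptions about draw counts and correlation at a 10% rate per draw, so none should be quoted as the expected bias. The co-primary outcomes, the sample size and the day 3 coagulation comparison are outside the point. It rests on reading the III.4.a times as applying to the laboratory arm, which the section structure and III.1 support. Label: cheap improvement.

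**What to change.** - Reconcile III.4.a with III.4.b, and resolve whether blood gases are at a fixed interval or at the provider's decision. Which schedule to adopt is for the sponsor.
- State one outcome-assessment schedule that applies to both arms, separate from tests ordered for care. Keep ROTEM-arm providers blinded to conventional coagulation results, as III.4.b already intends.
- Base the acidosis, blood-gas and day 1 coagulation comparisons on values at matched, protocol-specified times. For example, these could be baseline, a common intraoperative time and end of surgery, with 24 hours for coagulation. Name the summary measure for each, and treat unscheduled values as descriptive only.

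Restricting the analysis without naming common times would not be enough, because III.4.b currently gives the ROTEM arm no scheduled conventional draw to match against.

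The cost is mainly wording in the protocol and SAP. The downside is fewer usable time points, or a few added samples if the sponsor chooses them. Eligibility requires only an expected duration above 2 hours, so later intraoperative times would be reached only in longer operations, which limits the choice of a common one.
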